#### 5.3. Missing data

We will use the linear mixed model analyses, which provides unbiased effect estimates under the assumption that the outcome data is missing at random. In a sensitivity analysis, missing values will be imputed using a multivariate normal approach with 20 imputed data sets.

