#### 2.4. Determination of sample size

Previous studies show that the intervention effect in ISI from baseline to after intervention was 2.8-4.7 points in the intervention group compared to the control group (Vedaa et al., 2020; Wiklund et al., 2022). We therefore estimated that a sample size of 144 (72 in each group) was necessary to detect a 3-point difference with 90% power and a 2-sided alpha level of .05. Previous RCTs of dCBT-I report sample attrition rates between 12% and 50%(Christensen et al., 2016; Vedaa et al., 2020). To allow for a 30% dropout rate a 3-months follow-up, we aim to include 188 participants (94 participants in each arm) to answer our primary aim.

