#### 2.7. Stopping guidance

If the intended sample size is not reached during the intended recruitment period (ending 31 March 2025), the inclusion of participants will stop at 140 participants (70 participants in each arm), which will ensure adequate statistical power to detect a 3-point difference with 80% power, anticipating a 30% dropout rate during the follow-up.

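### The only missing-data sensitivity analysis assumes missing at random, as the primary model does, so it cannot show whether the 3-month ISI result survives dropout that is not at random

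*SAP*

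**What the plan says.** Section 5.3 of the SAP states that the linear mixed model "provides unbiased effect estimates under the assumption that the outcome data is missing at random". The next sentence gives the only analysis aimed at missing data: "In a sensitivity analysis, missing values will be imputed using a multivariate normal approach with 20 imputed data sets". The imputation variables are not listed, and no shift, reference-based, pattern-mixture or tipping-point step is mentioned there or elsewhere.

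Two other supplementary analyses are planned: an unadjusted version of the primary model (section 5.1.2) and a per-protocol analysis based on module completion (sections 3.2 and 3.3.2). Neither changes what is assumed about missing outcomes.

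The SAP expects substantial loss. Section 2.4 says "To allow for a 30% dropout rate a 3-months follow-up, we aim to include 188 participants", and notes that earlier trials of digital CBT-I "report sample attrition rates between 12% and 50" per cent. Section 2.7 lets recruitment end at 140, again "anticipating a 30% dropout rate during the follow-up". Section 3.3.1 keeps everyone randomised in the effectiveness analyses. Section 4.2 records non-response to the questionnaire as loss to follow-up and does not oblige participants to explain a withdrawal.

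**The concern.** With everyone randomised in the analysis and perhaps three in ten lacking the primary outcome, the result depends on an assumption about values that nobody sees. The SAP names that assumption, then checks it with a method that shares it. If participants who miss the 3-month questionnaire differ from what their observed data predict, and do so differently by arm, both analyses carry the same error.

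The arms plausibly have different reasons to stay. The app arm is asked to do self-managed work that includes sleep restriction (section 2.3.2), while controls are offered the app only after the 12-month follow-up (section 2.3.1). Because reasons for leaving may be unknown, the data cannot settle whether MAR holds. At stake is whether the report can say how far the primary conclusion depends on MAR.

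**Working it through.** **Inputs.** From the SAP: a 3-point difference, 90% power, two-sided alpha 0.05, 72 per arm before dropout, 188 randomised (94 per arm), fallback 140 (70 per arm), 30% dropout. Assumed: SD 5.5, equal dropout in both arms, an observed MAR estimate of exactly 3 points, and a standard error unchanged by the shift.

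**1. Is SD 5.5 reasonable?** The SAP gives no SD. Solving 3 = (1.960 + 1.282) x SD x sqrt(2/72) gives SD = 5.55. With SD 5.5, the sample size per arm is 71 by the normal formula and 72 by the t-test, so 5.5 agrees with the plan's 72 per arm.

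**2. Effect of a shift.** Let m be the missing share in an arm and delta the number of ISI points by which its dropouts are worse than MAR predicts. The benefit becomes 3 - (m_app x delta_app - m_control x delta_control). With a shift in the app arm only and m = 0.30:

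- delta 2: 3 - 0.6 = 2.4
- delta 4: 3 - 1.2 = 1.8
- delta 5: 3 - 1.5 = 1.5

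At delta 3, missing shares of 12%, 30% and 50% give 2.64, 2.10 and 1.50.

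**3. Delta at which significance is lost.** SE = SD x sqrt(2/n observed per arm); tipping delta = (3 - 1.96 x SE)/0.30. No benefit among app-arm dropouts means delta = 3, leaving 3 - 0.9 = 2.1.

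| Randomised | Observed per arm | SE | 1.96 x SE | Tipping delta | Range, SD 6 to 5 | z at 2.1 points |
|---|---|---|---|---|---|---|
| 188 | 94 x 0.7 = 65.8 | 0.959 | 1.88 | 3.7 | 3.2 to 4.3 | 2.19 |
| 140 | 70 x 0.7 = 49 | 1.111 | 2.18 | 2.7 | 2.1 to 3.4 | 1.89 |

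These SEs take no credit for baseline ISI. With an assumed baseline correlation of 0.5 they shrink by sqrt(1 - 0.25) = 0.866, to 0.830 and 0.962. The tipping deltas become (3 - 1.63)/0.30 = 4.6 and (3 - 1.89)/0.30 = 3.7, and z at 2.1 points becomes 2.53 and 2.18.

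**4. Can MAR imputation see the problem?** Simulation: 188 randomised, 30% missing per arm, SD 5.5, baseline correlation 0.5, 20 imputations, 1,500 repetitions. It used baseline and one follow-up, with a baseline-adjusted regression in place of the full mixed model.

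| Delta in app arm | Effect with complete data | MAR estimate | Imputation | Imputation plus matching delta |
|---|---|---|---|---|
| 0 | 3.01 | 3.00 | 3.00 | 3.00 |
| 2 | 2.38 | 2.99 | 2.99 | 2.39 |
| 4 | 1.81 | 3.02 | 3.02 | 1.81 |
| 6 | 1.17 | 2.96 | 2.97 | 1.17 |

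The MAR estimate and the imputation both stay near 3 while the complete-data effect falls. Only the shifted imputation follows it. Imputation and analysis used the same variables here, so this shows blindness to dropout not at random. It does not show that the SAP's two analyses must always agree.

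**The case against.** A reader might infer that the imputation must reproduce the mixed model apart from simulation noise and is therefore worthless. The SAP does not support that. Section 5.1.2 lists 3 and 6 months and only a participant random effect, which implies equal correlations over time. A multivariate normal imputation usually has an unrestricted covariance and could use the 6-week ISI shown in Table 1. In a simulation with a true effect of 3 and MAR dropout in the app arm driven by 6-week ISI (assumed SDs 4 to 5.5, correlations 0.35 to 0.7, about 30% missing), a model of the section 5.1.2 type gave 3.73. An unrestricted-covariance likelihood model using 6-week ISI, a large-sample stand-in for the imputation, gave 3.00. A further run gave 3.66 against 2.99. The planned check can therefore be informative about the covariance and the 6-week data. That objection stands, but the check remains a MAR analysis.

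Other objections also stand in part:

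- Section 5.3 says nothing false. It states its assumption and does not claim that the imputation tests departures from it.
- At 188 randomised, the tipping delta exceeds 3: app-arm dropouts would have to end up worse than comparable controls before significance is lost.
- Stopping the app is not the same as missing the questionnaire, and departures from MAR could go either way. Nothing in the SAP shows that dropout will be not at random, and 30% is a planning figure.
- A reader might also infer that 20 imputations are too few. Relative efficiency is 1/(1 + 0.30/20) = 98.5% at 30% missing information and 1/(1 + 0.50/20) = 97.6% at 50%, so this has little force.

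**Conclusion.** The point holds: the SAP names MAR as the basis of its primary estimate and plans no analysis that departs from it. The primary model itself stands, and the SAP gives no ground for saying that its estimate will be biased.

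Under the stated assumptions, the 3-point benefit falls by 0.3 points for each point of delta in the app arm. At 188 randomised the conclusion is fairly resistant: it tips at about 3.7, and the no-benefit case stays significant. At the fallback of 140 it is more fragile: it tips at about 2.7, and the no-benefit case falls just short of significance, although an adjustment worth a baseline correlation of 0.5 would restore it. A smaller observed effect would tip sooner. The SD, correlation and deltas are assumptions; the algebra of the shift and the shared MAR assumption do not depend on them. The plan should be changed on this point.

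**What to change.** In section 5.3, keep the multivariate normal imputation, run it separately by arm, list its variables and include 6-week ISI. Add a delta-adjusted (pattern-mixture) analysis of 3-month ISI: after imputation, add shifts to the imputed values, varied independently in the two arms (for example 0 to 5 points each), and refit the primary comparison. Report the estimate and confidence interval over the grid, and the delta at which the interval first includes zero.

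The shifts must vary by arm because an equal shift in both arms largely cancels when dropout is similar: at 30% in each, 0.30 x delta - 0.30 x delta = 0. Fix the grid before allocation is revealed, in keeping with section 1.1.

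The cost is a short loop after the imputation step in Stata and one supplementary table, with no new data. Raising the number of imputations is optional.

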# 5.4. Statistical software

All analyses will be performed using StataMP 18 (StataCorp. 2023. Stata Statistical Software: Release 18. College Station, TX: StataCorp LLC).

